- Breastfeeding mothers who have access to an Internet connection.
- Breastfeeding mothers who have the necessary equipment to access platforms with video-calling capabilities.
- Breastfeeding mothers who are proficient in the use of platforms with video-calling capabilities.

Exclusion Criteria:

- Mothers for whom breastfeeding is contraindicated.
- Breastfeeding mothers with a diagnosis of mental illness.
- Breastfeeding mothers who are or have been donors to the Human Milk Bank of the National Maternal and Perinatal Hospital.

Sampling for Intervention Development

Population: Breastfeeding mothers treated at the National Maternal and Perinatal Hospital (NMPH).

Sample Size: The sample size was determined using the OpenEpi program, with the option “Sample size to compare two means”, considering a IC of 95%, a power of 80%, a sample size ratio equal to 1, a minimum mean difference of 2.1 (in the breastfeeding knowledge score) and a SD of 3.4 for both groups, similar to that found in the study by Joshi et al (1).

Therefore, the net sample size required for this study was 86 participants, distributed as follows: 43 in the control group and 43 in the intervention group. However, considering a potential loss of 30% between the initial and the final assessment, the sample size was increased by 112 mothers in total.

Inclusion Criteria:

- Breastfeeding mothers within 40 days postpartum.
- Breastfeeding mothers with living children.
- Breastfeeding mothers with an active Internet connection.
- Breastfeeding mothers who possess the technological equipment required to access the innovative technological tool (smartphone, tablet, or computer).
- Breastfeeding mothers residing within the jurisdiction of the National Maternal and Perinatal Hospital.

Exclusion Criteria:

- Breastfeeding mothers who are illiterate.
- Breastfeeding mothers with a diagnosis of mental illness.
- Breastfeeding mothers with significant difficulties in operating technological equipment.
- Breastfeeding mothers who are current users of any milk bank.
- Breastfeeding mothers who are or have been donors to the Human Milk Bank of the National Maternal and Perinatal Hospital.

Techniques and procedures

The time of participation in the study will be approximately 3 months, divided into the following phases: enrollment (15 days), baseline assessment (7 days), exposure to the intervention (60 days), and final assessment (7 days).

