The development of the mobile intervention was based on the Human-Centered Design (HCD) approach (27). *AmamantApp* app includes modules on breastfeeding basics, benefits of breastfeeding for mother and child, breast milk donation, benefits of donating breast milk, myths and beliefs about human milk donation, requirements to be a donor, and where to donate.

To reduce bias, participants will be randomly assigned to the intervention and control groups in a 1:1 ratio according to their order of inclusion in the study. A master randomization list will be generated using the Spanish version of the free OxMaR software (28).

The intervention group will receive education on human milk donation via a mobile app, and the control group will receive information on human milk donation through printed leaflets. The app will be installed and explained to the mothers with hospital discharge orders on their mobile phones. The intervention will continue while the mothers are at home. The research team will hold an interactive session to introduce the mobile app to the participants. This will begin with an initial explanation of the app's features, followed by a period in which participants will be able to explore and use the application in real time. Furthermore, participants will receive weekly training on how to use the app to reinforce their knowledge of its operation.

The intervention period will last 60 days, during which knowledge, attitudes, and practices (KAP) will be assessed using a KAP questionnaire. This instrument will be administered face-to-face at baseline (pretest) and online via Google Forms after the intervention (posttest).

Design and Evaluation of the Mobile App

The process of designing the intervention with the Amamantapp app was based on Human Centered Design (HCD) through the application of the Design Thinking technique [29, 30]. This technique consisted of 6 stages:

Stage 1: Recognition

Aimed at empathizing, researchers defined the user profile, as well as the sociodemographic characteristics of the breastfeeding mothers. In this stage, 12 in-depth interviews were used to collect information concerning their KAP related to breastfeeding/breastmilk donation and the use of technology. At this stage, it was found that mothers were not aware that they

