With the final version of the technological innovation tool, the randomized controlled trial will be implemented for a period of 60 days. The research team will continuously conduct field evaluations of the tool's performance (verification) and ensure the maintenance of the intervention through push notifications, reminders, text messages (SMS), or other complementary resources. At this stage, a baseline and final measurement of indicators will also be assessed for both the intervention and control groups using a KAP questionnaire developed by the researchers. As part of this last stage, the qualitative component of the evaluation of the effect of the mobile intervention will be implemented. Purposive sampling will be used to recruit participants. Any breastfeeding mother from the intervention group who has completed the mobile intervention will be eligible to take part.

Analysis Plan

Qualitative Analysis Plan

The information gathered from the in-depth interviews will be transcribed, processed, and analyzed using specialized qualitative data analysis software. Consequently, matrices and graphic organizers will be generated.

Statistical Analysis Plan

The information collected during the intervention will be processed in MS Excel and analyzed using IBM SPSS statistical software.

Inferential analysis will be by intention to treat (ITT), to ensure the equivalence of the study groups. The sociodemographic and baseline characteristics of the control and intervention groups will be compared using Pearson's Chi-square test, Fisher's exact test, or Student's t-test, depending on the type of variable.

To determine the effect of the intervention, changes in milk donation knowledge scores among breastfeeding mothers in the intervention group will be compared with the control group throughout the study period (baseline and endline variation) using a double difference regression model.

For qualitative variables (attitudes, practices), a Cochran's Q test will be applied to evaluate changes following the intervention period. Regarding donation practices, Fisher's exact test will be applied, and the Odds Ratio (OR) will be calculated to determine the utility of the intervention in breast milk donation. Finally, only descriptive statistics will be presented regarding user satisfaction.

Ethical Considerations

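### The online knowledge posttest leaves room to look up answers to a different degree in each arm, and the plan neither limits nor records this

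*Combined protocol and SAP*

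**What the plan says.** Section VIII, Techniques and procedures, sets two modes for the same questionnaire: "This instrument will be administered face-to-face at baseline (pretest) and online via Google Forms after the intervention (posttest". The sentence just before it places the KAP assessment within the 60-day intervention period. The phase list at the start of the same section gives a sequence instead: "exposure to the intervention (60 days), and final assessment (7 days".

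On materials, the section says: "The app will be installed and explained to the mothers with hospital discharge orders on their mobile phones". The app's listed modules include myths about donation, donor requirements and where to donate. Weekly training in its use is planned, and Stage 6 (Effect Evaluation) adds push notifications, reminders and text messages. The control arm receives printed leaflets on milk donation. Eligibility requires an active Internet connection in both arms.

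The Statistical Analysis Plan says that "changes in milk donation knowledge scores among breastfeeding mothers in the intervention group will be compared with the control group", using baseline and endline values in a double difference regression. Attitudes are assigned Cochran's Q. Fisher's exact test and an odds ratio are added for donation practices, but no between-arm test is named for attitudes.

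The document does not say whether the app is removed or locked, or the leaflets collected, before the posttest. It describes no supervision, time limit, instruction to answer without materials, log of app use during the form, or sensitivity analysis for look-up.

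**The concern.** The first specific objective is the level of knowledge, and the sample size rests on a knowledge score. A face-to-face pretest leaves little room to consult anything. An online posttest leaves much more, and what lies within easy reach differs by arm: an app on the phone whose use has been reinforced for two months, or a paper leaflet. If mothers in one arm consult material more often, part of the estimated effect is access to information at the time of the test, not knowledge gained. Because this arises only at posttest, baseline scores cannot correct for it, and no planned data item would show whether it happened.

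A second, smaller issue concerns attitudes. Every pretest is face-to-face and every posttest is online, so a within-arm before-after test cannot separate a change in attitude from a change in how the question was put.

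**Working it through.** **1. Inputs.** Sampling for Intervention Development assumes 95% confidence, 80% power and equal arms. For the effect it takes "a minimum mean difference of 2.1 (in the breastfeeding knowledge score) and a SD of 3.4 for both groups". The result is 86 participants, that is, 43 per arm. Look-up rates and the points gained by look-up are not in the document, so every value used for them below is an assumption.

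**2. The plan's own figure.** Two-sided alpha 0.05 (sidedness is not stated):

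n per arm = 2 × [3.4 × (1.960 + 0.842) / 2.1]² = 41.15, rounded up to 42. The t-test version gives 42.13, rounded up to 43, so 86 in total. The stated figure reproduces. No corrected sample size follows from this point.

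**3. Timing.** Two statements (the phase list and the sentence on mode) put the posttest after the 60 days. One sentence puts the KAP assessment within them. They need reconciling. Neither reading says what happens to the app or the leaflets when the form is sent.

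**4. What the double difference removes.** Let m be a mode shift common to both arms, p_A and p_C the shares who look up answers at posttest (app, control), and g the average points gained by doing so, taken as equal in both arms. With comparable baselines:

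estimated effect = true knowledge effect + (m − m) + (p_A − p_C) × g

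The common mode shift cancels. The last term, b = (p_A − p_C) × g, does not.

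**5. Size under assumed values.** The false-positive rate is for no true knowledge effect, 43 per arm and a normal approximation, with SE = 3.4 × √(2/43) = 0.733. This treats the SD of the analysed quantity as 3.4. For change scores the SD is 3.4 × √(2(1 − ρ)), which equals 3.4 when the pre-post correlation ρ is 0.5; the document gives no ρ.

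| p_A − p_C | g (points) | b (points) | b / 2.1 | Two-sided false-positive rate |
|---|---|---|---|---|
| 0 | any | 0 | 0% | 5% |
| 0.10 | 2 | 0.20 | 10% | 5.9% |
| 0.20 | 3.4 | 0.68 | 32% | about 15% |
| 0.20 | 5 | 1.00 | 48% | 27.6% |
| 0.40 | 3.4 | 1.36 | 65% | about 46% |
| 0.30 | 5 | 1.50 | 71% | 53.4% |
| −0.20 | 3.4 | −0.68 | −32% | about 15%, favouring the leaflet |

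Worked row: 0.20 × 3.4 = 0.68; 0.68 / 2.1 = 32%; 0.68 / 0.733 = 0.927; P(Z > 1.960 − 0.927) + P(Z < −1.960 − 0.927) = 0.151 + 0.002 = 0.153.

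With 39 per arm (30% loss from 112 leaves about 78), the rate for b = 1.0 is 25.5% instead of 27.6%, so the picture does not depend on retention. In the last row, a true effect of 2.1 would appear as 2.1 − 0.68 = 1.42.

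**6. Attitudes.** Cochran's Q compares repeated binary responses within the same women. With one face-to-face and one online measurement, mode and time coincide exactly. A between-arm comparison would cancel a mode shift common to both arms, but none is specified for attitudes.

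**The case against.** The strongest reply is that most of this rests on silence, and several stronger readings go too far.

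- A reader might infer that exposure continues through outcome measurement. The document does not support that: the phase list and the mode sentence both place the posttest after the intervention. What stands is that no end of access is described and that one sentence conflicts on timing.
- A reader might infer an unsupervised form, left open for seven days and completed on the phone that carries the app. The text says only that the form is online and that the final assessment phase lasts seven days. It does not give the device, and eligibility admits smartphone, tablet or computer.
- A reader might infer that the bias must favour the app. Controls have leaflets on the same subject and Internet access, and app users who have learned the material may need to look up less. The direction is likely, not established.
- The questionnaire items are not in the document, so their overlap with the app's content is plausible but unverified. The 3.4-point gain borrows the SD of a breastfeeding knowledge score; the scale of this trial's researcher-developed questionnaire is not given.
- The change of mode is the same in both arms and does not by itself bias a between-arm contrast. The attitude problem comes from using a paired test and could equally be met by comparing arms.

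All of this limits the claim. It does not remove it: the plan as written permits look-up that differs by arm, the model does not correct for it, and nothing collected would reveal it.

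**Conclusion.** The point holds as an uncontrolled and undetectable threat to the knowledge outcome, not as a demonstrated bias. Its size is (difference in look-up share) × (points gained): zero if look-up is equal, 0.68 points or 32% of the design difference under a 20-percentage-point difference and a 3.4-point gain, and of opposite sign if controls look up more. These figures rest on assumed rates, an equal gain in both arms and an SD taken from another instrument, so they show scale and do not predict. The confounding of mode with time affects only the within-arm attitude analysis. The plan should be changed, because the remedy costs very little compared with the doubt it would otherwise leave over a positive knowledge result.

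**What to change.** 1. Reconcile the timing statements in Techniques and procedures, and state whether the app and the leaflets remain available when the posttest is sent.
2. Keep the online form. Put the same instruction at its head in both arms: answer without the app, the leaflet or the Internet.
3. Add one closing item asking whether any material was consulted and, if so, which.
4. Pre-specify a sensitivity analysis of the knowledge effect: report the consulted share by arm, subtract a range of assumed gains from the scores of mothers who report consulting, and refit the double difference model. Consultation occurs after randomisation, so simply excluding those mothers would not preserve the randomised comparison and should be supplementary at most.
5. If the backend allows it, suspend the app's educational modules until the form is submitted.
6. State that the within-arm attitude test cannot separate time from mode, and rest conclusions about attitude on a between-arm comparison.

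The cost is one instruction, one form item and one extra analysis, plus a backend setting if feasible. Consultation will be self-reported and probably under-reported, and a lock alone leaves controls with their leaflet, so it should accompany the common instruction and not replace it. Live interviewer calls are not needed. No blinding is described, so staff who may know the arm would be collecting attitude and practice answers, which exchanges one possible bias for another.

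### The KAP questionnaire moves from face-to-face to online between baseline and endline, and the only test named for attitude cannot separate a change in attitude from that change of mode

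*Combined protocol and SAP*

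**What the plan says.** Techniques and procedures fixes the mode of the KAP questionnaire at each time point: "This instrument will be administered face-to-face at baseline (pretest) and online via Google Forms after the intervention (posttest". No arm or subgroup is treated differently. Stage 6 (Effect Evaluation) confirms that both arms are measured with one instrument of the study team's own making ("a baseline and final measurement of indicators will also be assessed for both the intervention and control groups using a KAP questionnaire developed by the" …).

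The Statistical Analysis Plan then treats the outcomes differently:

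- **Knowledge:** "changes in milk donation knowledge scores among breastfeeding mothers in the intervention group will be compared with the control group", with the model given as "baseline and endline variation) using a double difference regression model".
- **Attitudes and practices:** "For qualitative variables (attitudes, practices), a Cochran's Q test will be applied to evaluate changes following the intervention period".
- **Donation practice, in addition:** "Regarding donation practices, Fisher's exact test will be applied, and the Odds Ratio (OR) will be calculated".

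Attitude is one of the three specific hypotheses, and Cochran's Q is the only test named for it. The documents describe no check that the two modes give equivalent answers, no bridging sample and no analysis that allows for mode.

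**The concern.** Every baseline answer is given in one mode and every endline answer in another. Within a mother, the effect of time (including any effect of the app) and the effect of mode are completely confounded, and no within-subject analysis can pull them apart.

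A comparison between randomised arms would deal with a mode effect that both arms share. Cochran's Q as written makes no such comparison, so randomisation does not protect the attitude result. Donating milk is a socially approved act, and it is plausible that mothers answer more favourably face-to-face than on an online form. If so, moving to the form would lower measured attitude at endline for reasons unrelated to the app. What is at stake is the answer to the second specific hypothesis: an improvement could be hidden, or a deterioration reported that did not occur.

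**Working it through.** **Inputs from the documents.** The modes are as quoted above, with 1:1 allocation. Sampling for Intervention Development gives 43 mothers per arm (86 in total), a difference of 2.1 and SD 3.4 on the knowledge score, 80% power and 95% confidence (taken as two-sided 5%).

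**The plan's own figure.** n per arm = 2(1.96 + 0.8416)² × 3.4² / 2.1² = 2 × 7.849 × 11.56 / 4.41 = 41.15, rounded up to 42. The t-based solution is 42.13, rounded up to 43. The stated 43 per arm reproduces and is used below.

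**Attitude, Cochran's Q.** With two time points, let b be the number of mothers switching to favourable and c the number switching to unfavourable. Then Q = (b − c)² / (b + c), and the test rejects at 3.841 or more.

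Assumptions, none of them from the documents: a binary attitude item, no true change, 5% of mothers switching up at random, and 5% + m switching down, where m is the net mode shift. The documents do not say whether Q is run per arm (n=43) or pooled (n=86), so both are shown.

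| Net mode shift m | Rejection rate, n=43 | Rejection rate, n=86 |
|---|---|---|
| 0% | 4.5% | 4.4% |
| 5% | 12% | 21% |
| 10% | 29% | 56% |
| 15% | 50% | 84% |
| 20% | 70% | 96% |

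Direction matters. At m = 10% and n=43, apparent deterioration accounts for almost all of the 29%, and apparent improvement for under 0.1 percentage points. At n=86 the share showing improvement is smaller still.

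Masking follows from the same set-up. Suppose the app truly moves a net 10% of mothers upwards (15% up, 5% down) and the mode moves a net 10% downwards (a further 10% down). The expected net change is 15% − 15% = 0, and the improvement disappears.

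Few mothers are needed. If all switches go one way, four of 43 give Q = 16/4 = 4, p = 0.0455; three give Q = 9/3 = 3, p = 0.083.

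A second model gives a similar picture. With a latent correlation of 0.5 and a baseline favourable proportion of 0.50, a pure mode shift to 0.60, 0.65 or 0.70 makes Q reject in about 19%, 39% and 62% of trials at n=43. The shift there is upward, but the test is symmetric in direction.

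**Knowledge, double difference.** Write m_T and m_C for the mode shift in the app and leaflet arms and δ for the true effect. The expected double difference is (δ + m_T) − m_C, which equals δ when m_T = m_C. Simulation with 43 per arm, SD 3.4 and an assumed baseline–endline correlation of 0.5 agrees:

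- Equal shift of 1 or 2 points, no true effect: mean double difference 0.00, type I error 5.1%.
- Equal shift of 1 point, true effect 2.1: estimate 2.10, power 81%.
- The same equal shifts tested within one arm, no true effect: rejection in 47% (1 point) and 96% (2 points).
- Shift differing between arms by 0.5, 1.0 or 2.1 points, no true effect: bias of that size, and rejection in 10%, 27% and 81%.

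A ceiling or change of spread common to both arms also leaves type I error at about 5%, because under the null the randomised arms have the same score distribution at each time point. Such an effect can rescale or attenuate a real difference; it cannot create one.

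**The case against.** The strongest reply is that the trial is randomised ("participants will be randomly assigned to the intervention and control groups in a 1:1 ratio") and both arms change mode together, so the control arm absorbs the mode effect. For knowledge, the outcome on which the trial is sized, this is right. A reader might infer that the mode change invalidates the knowledge result, or that a ceiling or altered spread would produce a false effect there. The documents do not support that: bias under the null needs a mode effect that differs by arm, and nothing in them shows one.

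Three other stronger readings also fail.

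- **A false claim of benefit.** If face-to-face answers are the more favourable, the bias runs against the app.
- **Lost power for knowledge.** Two modes might lower the baseline–endline correlation, but no correlation is given. Even an assumed fall from 0.6 to 0.5 takes change-score power from 89% to 81%, still above the planned 80%.
- **Practice equally affected.** The exclusion of current and past donors to the hospital's milk bank, and of current users of any milk bank, should keep baseline donation low however it is asked. Donation practice also gets Fisher's exact test and an odds ratio. If those compare arms at endline, which is not spelled out, both arms have answered in the same mode.

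It is also fair to say that the documents do not state that the endline form is completed unattended or at home, nor that the face-to-face questionnaire is read aloud. A mode effect is possible, not demonstrated.

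Finally, one can argue that the deeper weakness is Cochran's Q itself, which would also absorb time, retesting and leaflet effects. That stands, and is why the remedy cannot be a change of mode alone. None of this removes the problem for attitude, where no between-arm analysis is planned.

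**Conclusion.** The concern holds for attitude. Mode and time coincide for every mother, and the only named test is within-subject, so a change in attitude may include a mode effect and cannot be separated from it. Under the assumed 10% net shift and 5% random switching, a nominal 5% test rejects in about 29% of trials at n=43 and 56% at n=86 if arms are pooled, almost always as apparent deterioration. Over shifts of 5% to 20% the ranges are 12% to 70% and 21% to 96%. The size and direction of any shift are assumptions; the confounding itself is not.

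It does not extend to a claim that the knowledge double difference is biased under the null, and it is of little weight for donation practice. The point should be corrected, but it does not threaten the knowledge comparison on which the trial is sized.

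**What to change.** 1. **Use one mode.** In Techniques and procedures, replace the sentence on administration with, for example: *Each mother will complete the KAP questionnaire herself on the same Google Form before and after the intervention; at baseline, staff may confirm identity and supply the link but will not read out or prompt answers.* State the endline completion conditions for both arms.
2. **Compare arms for attitude.** In the Statistical Analysis Plan, base the attitude conclusion on endline attitude by arm adjusted for baseline, or on a group-by-time term. Do this whether or not the mode is changed, and for any baselines already taken face-to-face.
3. **Limit the within-arm results.** Do not interpret pre-to-post changes within an arm as effects of the app.

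The cost is small. The form has to be built anyway, and eligibility already requires an internet connection and a suitable device and excludes illiterate mothers and those with significant difficulty using such equipment. The sample size is unchanged. There may be a few more skipped items at baseline, which required-answer settings can limit. Staff presence at baseline would still leave some difference in conditions from endline, which is a further reason to make the second change as well as the first.

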could donate their breast milk, nor were they aware of the existence of HMB. The mothers also expressed a favorable attitude towards human milk donation, but stated that they had not engaged in that practice due to a lack of knowledge.

Stage 2: Identification of Needs

An empathy map was drawn up with the responses obtained to identify the needs of the users and the prioritization of the issues to be addressed regarding breastfeeding and milk donation. In this second stage, the mothers' need for easily accessible information on human milk donation, the requirements to be a donor, the mechanisms for donating, and the locations of human milk banks were identified.

Stage 3: Ideation of Solutions

A team of 6 researchers devised different innovative solutions (eg, digital educational booklet, mobile app, telephone counselling, SMS, and MMS), which were then evaluated using the impact and innovation matrix; a vote was taken considering the criteria of impact, innovation, added value, and scalability. Finally, the mobile app was the top-rated vote.

Stage 4: Prototyping

The intervention is prototyped as a mobile app, based on the HCD model [27,31]. This model comprises sequential phases that range from defining the user requirement, designing the proposal, and through the implementation, verification, and maintenance of the intervention with the mobile app. The prototype was developed following the sequence previously described, which involved outlining the didactic content, the bibliographic search for educational content, the search for graphic resources, and the design of the screens, sections, and navigation routes.

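### Knowledge is analysed as a double difference without baseline adjustment; ANCOVA on the same data targets the same effect with equal or better precision, by an amount the documents do not allow to be fixed

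*Combined protocol and SAP*

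**What the plan says.** Section VIII, Statistical Analysis Plan, compares changes in donation-knowledge scores between the arms "throughout the study period (baseline and endline variation) using a double difference regression model". It names no covariate and does not say how a mother's two scores are linked in the model. Techniques and procedures, and Stage 6 of the app evaluation, have the questionnaire given at baseline and again after the intervention, in both arms, so the baseline score will be available.

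The trial was sized under Sampling for Intervention Development with the OpenEpi option "Sample size to compare two means", "considering a IC of 95%, a power of 80%, a sample size ratio equal to 1", and "a minimum mean difference of 2.1 (in the breastfeeding knowledge score) and a SD of 3.4 for both groups". The result is that "the net sample size required for this study was 86 participants", 43 in each arm, raised to 112 for a 30% loss. No pre-post correlation is given, and the text does not say whether 3.4 describes a score at one time or a change.

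**The concern.** A double difference analyses each mother's change, and a change score carries the noise of two measurements. If the pre-post correlation is low and the baseline is as variable as the endline, the change has a larger SD than the endline score. A trial sized on the endline SD would then be short of power. ANCOVA lets the data set the weight given to baseline instead of fixing it at one.

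Knowledge is the outcome used for sizing, so its model decides whether the planned power is reached. A low correlation is conceivable here. The design-stage interviews found mothers unaware that they could donate, "nor were they aware of the existence of HMB", and the questionnaire moves from face-to-face to online. Neither fact supplies a value of r.

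**Working it through.** **Inputs from the documents.** Difference 2.1, SD 3.4, 80% power, 95% confidence, 1:1 allocation, 43 per arm net, 112 in total after the loss allowance.

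**Assumptions.** Two-sided 5% test (sidedness is not stated); r from 0 to 0.7; baseline SD of 3.4 or 1.7. The documents give no r and no baseline SD.

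**Step 1: reproduce the plan's figure.** Normal approximation: n = 2 × [3.4 × (1.960 + 0.842) / 2.1]² = 41.15, or 42 per arm. With the t distribution, power is 79.9% at 42 and 80.8% at 43, so 43 per arm reproduces as a plain comparison of two means with no correlation term.

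**Step 2: variances.** Let s0 be the baseline SD and s1 the endline SD.

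- Double difference: variance of change = s0² + s1² − 2·r·s0·s1.
- ANCOVA: residual variance = s1²(1 − r²).
- Double difference minus ANCOVA = s0² − 2·r·s0·s1 + r²·s1² = (s0 − r·s1)², which cannot be negative.

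With s0 = s1 = s these become 2s²(1 − r) and s²(1 − r²), and ANCOVA's variance is (1 + r)/2 times that of the double difference. ANCOVA spends one extra degree of freedom (83 instead of 84 at 43 per arm), which is negligible.

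**Step 3: power at 43 per arm if 3.4 is the SD of the score.** Noncentral t, difference 2.1, endline SD 3.4.

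| r | Double difference, baseline SD 3.4 | Double difference, baseline SD 1.7 | ANCOVA (either baseline SD) |
|---|---|---|---|
| 0.2 | 61.0% (SD of change 4.30) | 78.9% (3.48) | 82.4% (residual SD 3.33) |
| 0.3 | 66.7% (4.02) | 82.8% (3.31) | 84.3% (3.24) |
| 0.5 | 80.8% (3.40) | 90.5% (2.94) | 90.5% (2.94) |
| 0.7 | 95.5% (2.63) | 96.8% (2.52) | 97.7% (2.43) |

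Example, r=0.3, equal SDs: 3.4 × √(2 × 0.7) = 4.02 for change and 3.4 × √(1 − 0.09) = 3.24 for ANCOVA. With baseline SD 1.7 the change variance is 2.89 + 11.56 − 2 × 0.3 × 1.7 × 3.4 = 10.98, SD 3.31. At r=0.5 the two methods coincide because 1.7 − 0.5 × 3.4 = 0.

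With equal SDs the double difference matches the plan's own two-mean calculation at r=0.5, where the SD of change equals 3.4, and falls below it at lower r.

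**Step 4: power at 43 per arm if 3.4 is the SD of change.** The double difference then has the planned 80.8% whatever r is. With equal SDs, ANCOVA's residual SD is 3.4 × √((1 + r)/2), that is 2.74, 2.94 and 3.13 at r=0.3, 0.5 and 0.7. Power is 94.0%, 90.5% and 86.7%.

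**Step 5: if the full 30% is lost.** 112 is 86 × 1.3, so a 30% loss leaves 112 × 0.7 = 78.4, about 39 per arm. With 3.4 as the endline SD, ANCOVA power is 76.8% at r=0, 78.5% at r=0.2 and 80.6% at r=0.3. With equal SDs the double difference has 62.4% at r=0.3.

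**The case against.** The strongest reply is that the plan contains no demonstrable mismatch. A two-means calculator sizes a comparison of mean changes as readily as one of endline scores, and the plan may have meant "a SD of 3.4 for both groups" as the SD of change. This stands. The documents cannot settle it, and on that reading the planned power is intact.

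Second, a reader might infer from the Stage 1 interviews that r is low because of a floor, and hence that power is near 60%. The two halves of that inference pull against each other: a floor also compresses the baseline SD, and the middle column of the table shows that most of the loss then disappears. The evidence for a floor is also thin. It comes from 12 qualitative interviews, whereas the Lima survey in National Background reports that 75.7% had heard of milk banks. The questionnaire's items and range are not given. This objection stands too.

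Third, a reader might infer that the regression will be run on stacked rows that treat a mother's two scores as independent. In that form power would be about 52–54% at 43 per arm for r from 0 to 0.7, and the true type I error about 0.5% at r=0.5. The plan does not say this. It speaks of comparing changes, which fits a within-mother analysis at least as well. What remains is a request to specify the model.

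None of this gives a reason to prefer the double difference. It is a recognised and unbiased method, but ANCOVA is at least as precise in every case above, apart from the one degree of freedom.

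**Conclusion.** The point holds as one of precision. The plan collects a baseline score and does not put it to its most efficient use. At 43 per arm with 3.4 as the endline SD, the power gained by ANCOVA runs from nothing (baseline SD 1.7, r=0.5) to about 21 percentage points (equal SDs, r=0.2: 82.4 − 61.0). If 3.4 is the SD of change and the two SDs are equal, the gain is about 6 to 13 points for r from 0.7 down to 0.3.

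The documents do not show that the trial is underpowered as planned. That would need 3.4 to be the SD of the score, a low r, and a baseline SD not much smaller than the endline SD. Nor would it be right to say that ANCOVA guarantees 80%: at 39 per arm it falls below when r is about 0.2 or lower.

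All the power figures also borrow 2.1 and 3.4 from a breastfeeding knowledge score in the cited education study, whereas the analysed outcome is donation knowledge on the researchers' own questionnaire. They show the relative merit of the two methods better than they show the power this trial will have.

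**What to change.** In the Statistical Analysis Plan:

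- Make ANCOVA the main knowledge analysis: endline donation-knowledge score regressed on arm and baseline donation-knowledge score, reporting the adjusted mean difference with its 95% CI.
- Keep the double difference as supportive only, fitted on within-mother changes or with mother as a random effect or cluster.
- Name any further covariates in advance, and do not choose them from the planned baseline significance tests.

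In the sample size paragraph, state whether 3.4 is the SD of the endline score or of the change, and give the correlation assumed if one is used.

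The cost is wording. The baseline score is already collected, the number of mothers does not change, and SPSS, already the planned software, fits the model.
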